5.1.2 Demographic and Baseline Characteristics

The demographic and baseline characteristics will be summarized based on the Safety Population. For quantitative variables, mean, standard deviation, median, and minimum/maximum values will be provided. For qualitative variables, the frequency and percentage will be provided.

5.1.3 Efficacy Analyses

Efficacy data and analyses will be performed on the Treated Population. As a sensitivity analysis, the analysis of the primary efficacy endpoint will also be performed on the Efficacy Evaluable Population.

5.1.3.1 Analysis of Primary Efficacy Endpoint

The primary efficacy endpoint is the proportion of subjects achieving complete immune tolerance during the ITI Treatment Phase and will be compared to the historical spontaneous remission rate of 10%.

The proportion of subjects achieving complete immune tolerance receiving Alphanate during the ITI Treatment Phase will be calculated along with the 95% confidence interval (CI). The exact (Clopper-Pearson) method for the binomial proportion will be used to calculate the 95% CI (21). If the lower bound of the 95% CI is greater than 10%, then it is statistically significant that the proportion of subjects achieving complete immune tolerance receiving Alphanate is greater than the historical spontaneous remission rate of 10%.

5.1.3.2 Analysis of Secondary Efficacy Endpoints

The proportion of subjects achieving either complete or partial immune tolerance within 33 months of ITI treatment will be summarized with the number, percentage, and 95% CI for the percentage.

Duration of maintenance of complete and partial immune tolerance will be summarized with mean, standard deviation, median, and minimum/maximum values.

Time to achieving inhibitor titer <0.6 BU, time to complete immune tolerance, and time to partial immune tolerance will be summarized using the Kaplan-Meier method.

Factor VIII inhibitor titer, FVIII:C recovery, and FVIII:C half-life will be summarized with mean, standard deviation, median, and minimum/maximum values by visit.

Frequency of bleeding events will be summarized by severity and annualized for the duration of each phase of the clinical trial. For subjects who achieved complete or partial immune tolerance, a similar analysis will also be performed for the annualized Prophylactic Phase.

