One retrospective study was performed at 11 US institutions where patients had received Alphanate for ITI (3). Data collection started in 2007 from patients who received ITI between 1997 and 2010. Primary ITI treatment was carried out in 8 patients, and rescue ITI was completed in 25 patients. The dosing regimen was 100 to 200 IU/kg/day for 7 of the primary ITI patients, while one of them received 50 IU/kg/day. All of the primary ITI patients were <16 years of age at the time of inhibitor diagnosis, and the median age at the time of initiation of primary ITI treatment was 41 months. This retrospective study provides the basis for adding prospective, clinical trial data to the existing knowledge base. Similarly, retrospective data were collected in an international (Spain, Italy, and Germany), multicenter, observational study to assess outcomes in patients with moderate to severe hemophilia A who developed inhibitors and were subsequently treated with Fanhdi for primary or rescue ITI (9,16). Adults and children (age <18 years) with moderate to severe congenital hemophilia A (FVIII:C <2%) with inhibitors treated with Fanhdi for primary or rescue ITI were included in the study. Treatment regimens varied widely (38 IU/kg 3 times per week to 300 IU/kg twice a day), although most patients received ≥ 100 IU/kg/day. All study data were collected via retrospective chart review of patients with known ITI outcomes. A total of 41 patients received primary ITI and 19 patients received rescue ITI. Of the primary ITI patients, 88% achieved complete or partial success, generally following the International Consensus Guidelines definitions for complete and partial success (7). Of the rescue ITI patients, 73% achieved complete or partial success. Median time to complete success was 19 months; median time to partial success was 22 months.

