3.3 Treatments

3.3.1 Treatments to be Administered

Subjects will start treatment with Alphanate 100 IU/kg/day with a one-time option to increase to a dosing regimen of 200 IU/kg/day at any time after 90 days of ITI treatment if inhibitor titer has decreased <20% of the level from the initiation of Alphanate ITI treatment *or* if there has been an increase in the rate of bleeding events relative to the rate of bleeding events experienced during the first 90 days of treatment *or* if the inhibitor titer increases to >500 BU following the initiation of Alphanate ITI treatment. Increased bleeding may be treated with bypass agents (Section 3.4); however, the dose of Alphanate may not be increased until after 90 days of ITI treatment. Following this 90-day treatment/ observation period, a possible increase in the rate of bleeding events relative to the rate during the 90-day observation period will be assessed at each clinic visit, which at any given time will allow for the dosage increase to 200 IU/kg.

The drug is administered by bolus intravenous injection daily until complete immune tolerance is achieved (Section 3.5.1.2) or for 33 months if complete immune tolerance is not achieved.

When subjects being treated at 100 IU/kg/day enter the Prophylactic Phase, the dose will be tapered down in a step-wise manner over an 8-week period to reach a final prophylactic dose of 50 IU/kg every other day or 3 times per week, at the investigator's discretion. During this taper period, the subject will receive:

- Alphanate 50 IU/kg/day for the first 4-week period
- Alphanate 50 IU/kg every other day for the second 4-week period

When subjects being treated at 200 IU/kg/day enter the Prophylactic Phase, the dose will be tapered down in a step-wise manner over a 12-week period to reach a final prophylactic dose of 50 IU/kg every other day or 3 times per week, at the investigator's discretion. During this taper period, the subject will receive:

- Alphanate 100 IU/kg/day for the first 4-week period
- Alphanate 50 IU/kg/day for the second 4-week period
- Alphanate 50 IU/kg every other day for the third 4-week period

After completing the taper period, the subject will receive the prophylactic dose regimen of 50 IU/kg every other day or 3 times per week, at the investigator's discretion, for the remainder of the 12-month Prophylactic Phase. Subjects completing the 12-month Prophylactic Phase will have completed the study.

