3.5.1.3 Secondary Efficacy Endpoints

The following are secondary efficacy endpoints:

- The proportion of subjects who achieve either complete or partial immune tolerance within 33 months of receiving Alphanate for ITI
- The proportion of subjects who maintain complete immune tolerance or partial immune tolerance without relapse (Section 3.5.1.4) for 12 months
- The annualized frequencies of bleeding events during the ITI Treatment Phase and the Prophylactic Phase

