3.6 Assessments

3.6.1 Assessment Periods

The study consists of 2 phases:

- A 33-month ITI Treatment Phase in which all eligible subjects will receive ITI treatment with Alphanate for a period of up to 33 months. The ITI Treatment Phase begins with a Screening Visit occurring up to 30 days before start of ITI treatment. Upon confirmation of successful immune tolerization, subjects will then enter the Prophylactic Phase (immediately for complete success subjects; after 33 months of ITI for partial success subjects).
- A 12-month Prophylactic Phase for all subjects who meet the criteria for complete or partial success to continue on a prophylactic dosing regimen of Alphanate.

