3.9 Removal of Subjects

Subjects may withdraw or be withdrawn from the study for the following reasons:

- At their own request or at the request of their legally acceptable representative
- If, in the investigator's opinion, continuation in the study would be detrimental to the subject's well-being
- At the specific request of the sponsor

Also subjects must be withdrawn for the following reasons:

- Subject is determined to be a treatment failure at the completion of 33 months of ITI treatment (Section 3.5.1.2).
- Subject has as a confirmed relapse in the Prophylactic Phase in which there is a concomitant loss of clinical response to FVIII therapy.
- Subject develops an infection with HAV, HBV, HCV, or HIV during the study.
- Subject develops a concomitant disease which, either because of its severity or duration or because it requires a change in treatment, contravenes the condition of the study.
- Subject is noncompliant with the protocol per the investigator's discretion.

In all cases, the reason for withdrawal must be recorded in the eCRF and in the subject's records.

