5 STATISTICAL METHODS AND DETERMINATION OF SAMPLE SIZE

5.1 Statistical and Analytical Plans

Data handling and evaluation procedures will be described in the Statistical Analysis Plan.

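### The maintenance endpoint is a 12-month proportion without relapse, but the supplied text specifies no analysis of that proportion, only a summary of a duration with no censoring rule

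*Combined protocol and SAP*

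**What the plan says.** Section 3.5.1.3 lists as a secondary endpoint "The proportion of subjects who maintain complete immune tolerance or partial immune tolerance without relapse" for 12 months, with relapse defined in section 3.5.1.4. The synopsis repeats this endpoint, and section 2.2 makes maintenance a secondary objective.

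On analysis, section 5.1.3.2 says "Duration of maintenance of complete and partial immune tolerance will be summarized with mean, standard deviation, median, and minimum/maximum values". That is the only analysis sentence on maintenance, and the synopsis statistical methods contain none. The same section plans a number, percentage and 95% CI for the other secondary proportion (complete or partial tolerance within 33 months), and Kaplan-Meier for the times to a negative titer and to complete and partial tolerance.

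Three other places bear on the point:
- Section 3.3.1, on the end of follow-up: "Subjects completing the 12-month Prophylactic Phase will have completed the study".
- Section 3.9, which lets subjects leave for reasons other than relapse, for example "At their own request or at the request of their legally acceptable representative". It requires withdrawal for a confirmed relapse only when clinical response to FVIII is also lost.
- Section 5.1.3, on the population: "Efficacy data and analyses will be performed on the Treated Population". It does not say how subjects who never achieve tolerance count for maintenance.

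**The concern.** The endpoint is a yes/no outcome per subject, while the stated analysis describes a length of time. Carrying out section 5.1.3.2 as written does not produce the percentage that section 3.5.1.3 defines.

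The duration is also limited by the design. A subject who stays relapse-free through Month 12 has a duration known only to be at least 12 months, and a subject who leaves relapse-free at Month 6 has one known only to be at least 6 months. Mean, SD, median and range treat such values as if they were observed relapse times. The section gives no start point, end point or censoring rule to prevent this. Study exit cannot serve as the relapse date either, because a subject who relapses without losing clinical response need not be withdrawn.

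At stake is the reading of durability, a stated secondary objective in an open-label, single-arm trial. If the denominator and the handling of withdrawals are not fixed beforehand, they could be chosen after the outcomes are known.

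**Working it through.** The plan gives no figure for this endpoint, so there is none to reproduce. The check asks whether the stated summaries determine the endpoint.

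**Inputs**
- Treated subjects: 25 (section 5.2).
- Subjects entering the Prophylactic Phase: not given, so assumed. The planning rate of 35% (section 5.2) gives 0.35 × 25 = 8.75, taken as 9, for complete tolerance only. Section 5.2 also cites prior complete-success rates of about 25 to 40%, giving 6.25 to 10 of 25, taken as 6 and 10. A high figure comes from section 1.2, on the comparable product: "Of the primary ITI patients, 88% achieved complete or partial success", so 0.88 × 25 = 22.
- Early exits: the documents give no rate. Two exits at Month 6 are used as an illustration.
- Time runs from Prophylactic Phase entry, and withdrawals are entered at their observed time (assumptions).

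**Duration summaries for n entrants, n − 2 at 12 months and two at 6 months**
- Mean = [12(n − 2) + 6 × 2] / n. For n = 9: (84 + 12)/9 = 10.67.
- SD = √{[(n − 2)(12 − mean)² + 2(6 − mean)²] / (n − 1)}. For n = 9: √[(12.44 + 43.56)/8] = √7 = 2.65.
- The median is 12 and the minimum is 6 in every row below.

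None of these uses the reason for the exit.

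**Kaplan-Meier relapse-free at 12 months**
- Both exits are relapses: 1 − 2/n.
- Both exits are relapse-free withdrawals: no events, so 100%.

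| Entrants | Mean | SD | Median | KM, both relapsed | KM, both withdrew relapse-free |
|---|---|---|---|---|---|
| 6 | 60/6 = 10.00 | √(48/5) = 3.10 | 12 | 66.7% | 100% |
| 9 | 10.67 | 2.65 | 12 | 77.8% | 100% |
| 10 | 108/10 = 10.80 | √(57.6/9) = 2.53 | 12 | 80.0% | 100% |
| 22 | 252/22 = 11.45 | 1.77 | 12 | 90.9% | 100% |

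In each row one set of summaries fits two different relapse results.

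**No early withdrawal.** Every time below 12 months is then a relapse, and the mean is a valid mean relapse-free time restricted to 12 months. The proportion maintained is still a separate quantity that no sentence asks for.

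**Precision and denominator of the proportion (Clopper-Pearson 95% CI)**
- 7 maintained of 9 entrants: 77.8% (40.0% to 97.2%).
- The same 7 of 25 treated: 28.0% (12.1% to 49.4%).

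**The case against.** The strongest reply is that the Statistical Analysis Plan will supply what is missing, since section 5.1 says "Data handling and evaluation procedures will be described in the Statistical Analysis Plan". This limits the claim. A reader might infer that the endpoint will go unreported, but the documents do not support that: the endpoint is plainly defined as a proportion, and the text of the plan to which section 5.1 defers is not supplied. What stands is that the supplied text specifies no analysis of the proportion and does state a different method.

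A second reply is that a duration cut off at Month 12 or at withdrawal is nowhere written. That is correct. The cut-off is inferred from the length of follow-up and the withdrawal rules, and the failure to separate relapse from withdrawal holds only if withdrawals are entered at observed time. No other handling is stated.

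A third reply is that without early withdrawal the mean is sound and Kaplan-Meier at Month 12 equals the simple proportion. Both are true, and neither adds the missing percentage.

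A fourth is that Kaplan-Meier will be coarse, because titer and recovery are scheduled only at Months 1, 2, 3, 4, 6, 8, 10 and 12. This is a fair reason to keep it supportive.

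Finally, this is a descriptive secondary endpoint with no planned test, so the consequence is limited.

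**Conclusion.** The point holds: the endpoint is a 12-month proportion without relapse, no analysis of it is specified in the supplied text, and the stated duration summaries cannot replace it. With 9 assumed entrants and two illustrative exits at Month 6, identical summaries are compatible with 77.8% or 100% relapse-free by Kaplan-Meier. The exit count, its timing and the entry of withdrawals at observed time are assumptions. The primary analysis and the sample size are not affected.

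Four stronger inferences are not supported:
- **Nine entrants as a minimum.** It is a planning value for complete tolerance. The rates cited in section 5.2 allow about 6 to 10, and partial responders would add to that. The 88% behind 22 entrants comes from a retrospective review of patients with known outcomes on another product, so it may be optimistic here.
- **The gap between 77.8% and 28.0% as an error in the plan.** The two percentages answer different questions. The natural reading of section 5.1.3 is that non-achievers count as not maintained; the defect is that this is left unsaid.
- **A median of 12 months as concealment by itself.** With 9 entrants the median stays at 12 with up to 4 relapses, but the mean, SD and minimum are also planned and would move.
- **The timing of phase entry as a reason why exit cannot date relapse.** Section 3.6.1 has entry "immediately for complete success subjects; after 33 months of ITI for partial success subjects". That bears on where the duration starts. Only the withdrawal rule in section 3.9 bears on the relapse date.

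**What to change.** In section 5.1.3.2:
- Add the number, percentage and Clopper-Pearson 95% CI of subjects maintained without relapse at 12 months. Label each denominator: subjects entering the Prophylactic Phase, and the Treated Population with non-achievers counted as not maintained, in line with section 5.1.3.
- Count relapse-free withdrawals as not maintained. Because that alone does not distinguish them from relapses, also show three counts: maintained, relapsed, and withdrawn without relapse.
- Analyse duration by Kaplan-Meier from Prophylactic Phase entry to confirmed relapse, censored at withdrawal or phase end. State that the proportion is the endpoint and this analysis is supportive.

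The cost is one paragraph and one table. Relapse results (section 3.6.2.5) and withdrawal reasons (section 3.9) are already collected, so no new data are needed. The drawbacks are a wide interval, a proportion that may fall below the Kaplan-Meier estimate (with two withdrawals and no relapse, 77.8% against 100% at 9 entrants), and coarse relapse times.

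A separate item, to be settled on its own: Appendix 1 footnote l requires recovery and half-life to confirm a suspected relapse, while sections 3.6.2.5 and 3.6.4.7 call for a repeat titer and recovery. These should be reconciled, since they decide who counts as relapsed.

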5.1.4 Safety Analyses

Safety analyses will be performed on the Safety Population.

Physical examination findings will be summarized.

The incidence of AEs, AEs by causality, AEs by severity, ARs, and suspected ADRs will be summarized. Subjects with deaths, SAEs, and AEs leading to premature discontinuation from the study will be listed.

The incidence of AEs of special interest (ie, central venous access and catheter-related complications for which the device was placed or was used for FVIII administration within the trial, infusion-site reactions, thromboembolic events, and hypersensitivity reactions) will be reported as related to study drug and will be summarized.

The severity of bleeding events will be summarized.

For all laboratory tests, the Screening and/or Baseline value and the change from Baseline will be summarized for numeric results, and frequency/percentage will be summarized for qualitative results. For those tests with normal ranges, shift tables will be provided. For virus safety test results, a data listing will be provided.

Summary statistics will be provided for the original value and change from baseline values for vital sign parameters.

5.2 Determination of Sample Size

The study by Caram et al (22) indicated that among patients with very high maximum inhibitor titers (≥ 10 BU), the spontaneous remission rate was 3.4% (1 of 29), with the upper limit of the 95% CI being 10%. Considering the various factors in estimating the true spontaneous remission rate for this population, a 10% spontaneous remission rate is considered a historical control. The Kurth et al publication (3) summarized the retrospective

```
CONFIDENTIAL
```

review of Alphanate when used for primary ITI treatment and reported complete success in 3 of 8 primary ITI patients. Using the same criteria for defining "complete success" as those in the current study and a Treated Population analysis approach, the complete success rate reported in the International Immune Tolerance Study (1) and in the North American Immune Tolerance Registry (14) was in the range of approximately 25 to 40%. Assuming that the rate for achieving immune tolerance is 35% with Alphanate treatment based on these publications, 25 subjects would provide 80% power to demonstrate a statistically significant improvement with a one-sided test at alpha level of 0.025 in a Treated Population analysis.

6 ADMINISTRATIVE

6.1 Investigators, Other Study Personnel, and External Committees

Information regarding additional key personnel involved in the conduct of the study, including names and contact details of participating investigators, monitors, clinical laboratories, technical departments and/or institutions, as well as information on members of additional study committees, will be found in the study files of the sponsor and at the investigator study center within the study reference manual/file.

Investigators and staff will receive training via an investigators' meeting, study center initiation visit or other appropriate individual study center training session(s).

6.2 Data Quality

Monitoring and auditing procedures defined/agreed by the sponsor will be followed to comply with ICH GCP guidelines. Each study center will be visited at regular intervals by a monitor to ensure compliance with the study protocol, ICH GCP and legal aspects. The on-site verification of the eCRF for completeness and clarity will include cross checking with source documents and clarification of administrative matters. Query verification of data will be described in the Data Management Plan.

6.3 Documentation

The study data will be recorded and kept current in the eCRF by the study center personnel directly responsible for the information. Entries made in the eCRF must be verifiable against source documents or have been directly entered into the eCRF, in which case the entry in the eCRF will be considered the source data.

The data in the eCRF will be monitored at the study center by Grifols representatives at regular intervals, reviewed for completeness, and compared with the source documents. Examples of source documents include individual subject medical records, which are separate from the eCRFs.

All AEs and SAEs must be recorded. All SAEs must be recorded on the SAE form. The SAE form must be kept in study center records with a copy provided to the designated person as detailed in the study file.

6.3.1 Record Retention

At study completion, all study data will be transferred to Grifols according to ICH GCP guidelines, local laws, regulations, and Grifols requirements. The study file and all source data should be retained until notification is given by the sponsor for destruction.

An investigator is required by ICH GCP guidelines to retain the study files. If an investigator moves, withdraws from an investigation, or retires, the responsibility for maintaining the records may be transferred to another person (eg, other investigator). Grifols must be notified in writing of the person responsible for record retention and the notification will be retained in the sponsor study file and the investigator study center file.

6.3.2 Access to Information for Monitoring

The data will be recorded and kept current in the eCRFs by the center personnel directly responsible for the information and reviewed for completeness by the monitor. Grifols personnel or designee can review the records.

In accordance with ICH GCP guidelines, the monitor must have direct access to the investigator's source documentation to verify the data recorded in the eCRFs for completeness, consistency, and accuracy and to verify adherence to the protocol. "Source documentation" includes individual subject files, separate from the eCRFs. Source documentation should be maintained and include visit dates, laboratory results, concomitant treatments, vital signs, medical history, examinations, AEs, IP dispensing logs, and other notes as appropriate. The investigator agrees to cooperate with the monitor to ensure that any problems noted during the course of these monitoring visits are resolved.

